### **8.7 Annual Reports**

In addition to the above reporting the CI will submit once a year, throughout the trial, or on request a progress/safety report to the Research Ethics Committee and R&D.

## **9. STATISTICS**

### **9.0.1 Responsibilities**

The research team consisting of the PI and research investigators will perform the data analysis and complete the write up.

### **9.0.2 Hypotheses**

We aim to evaluate the method of manufacturing CAD/CAM insoles from a direct-scan, compared to that of a foam-box cast. The null hypothesis is that the change in FHSQ Pain score pre and post-treatment will not differ between the treatment groups. The alternative hypothesis is that the change in FHSQ pain score will differ between groups.

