## 2. SYNOPSIS

|                      |   |
|----------------------|---|
| Study Title          | Comparing the effectiveness of computer-aided-design computer-aided-manufacture (CAD/CAM) insoles manufactured from foam-box cast vs direct scan on patient reported outcome measures: A double-blinded, randomised controlled trial  |
| Internal ref. no.    | R&I no GN22OR165  |
| Type of study        | A single centre, double blinded, randomised controlled trial  |
| Trial Design         | Interventional, equivalence Trial design.   |
| Trial Participants   | Participants with a medical condition or lower limb biomechanical deficit which would commonly be treated with the use of insoles, as per the NHS Greater Glasgow and Clyde MSK Foot and Ankle Pathway:
http://www.clinicalknowledgepublisher.scot.nhs.uk/Published/PathwayViewer.aspx?fileId=119  |
| Planned Sample Size  | 114 (57 per group)  |
| Follow-up duration   | Total duration of individual participant involvement: 14-16 weeks total. Including initial assessment and fitting 2-4 weeks, and 12-week follow-up.  |
| Planned Trial Period | Total Project length: 12 Months
Expected Recruitment Start date: 29/09/2022
Expected Recruitment End date: 29/06/2023
Anticipated Trial End Date (all participants completed recruitment, completed intervention, completed all follow up, all data collected and all issues resolved): 29/09/2023   |
| Primary Objective    | To compare the changes in pain in two groups of participants fitted with custom CAD/CAM insoles manufactured using different foot shape capture methods   |

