## 5. OBJECTIVES AND OUTCOME MEASURES

| Objectives  | Outcome Measures   | Timepoints of evaluation of this outcome measure (as applicable)   |
|---|--|--|
| 
 
Primary Objective
 
 
To compare the changes in pain in two groups of participants fitted with custom CAD/CAM insoles manufactured using different foot shape capture methods
  | 
Foot Health Status Questionnaire (Appendix 1) (FHSQ) – Pain sub-domain. The minimal important difference has a threshold of a 12.5 point change for pain
  | 
Completed at the Second Appointment, Third Appointment, Fourth Appointment and Fifth Appointment
  |
| 
Secondary Objectives
 
 
1. To compare the changes in foot function in two groups of participants fitted with custom CAD/CAM insoles manufactured using different foot shape capture methods
 
2. To compare the changes in foot health in two groups of participants fitted with custom CAD/CAM insoles manufactured using different foot shape capture methods
 
3. To compare the participant satisfaction in two groups of participants fitted with custom CAD/CAM insoles manufactured using different foot shape capture methods
 
4. To compare the time-in-transit and cost-time analysis
 
 | 
 
1. Foot Health Status Questionnaire – Function sub-domain. The minimal important difference has a threshold of a 7.1 point change for foot function
 
2. Foot Health Status Questionnaire – foot health sub-domain. The minimal important difference has a threshold of a -0.4 point change for foot health
 
3. Orthotic and Prosthetic User Survey (OPUS) Satisfaction with device survey (Appendix 2)
 
4. Time-in-transit – Measurement of
 
 | 
 
1. Completed at the Second Appointment, Third Appointment, Fourth Appointment and Fifth appointment
 
2. Completed at the Second Appointment, Third Appointment, Fourth Appointment and Fifth appointment
 
3. Completed at the fifth appointment
 
4. Throughout duration of trial
 
 |

|   |  |  |
|---|--|--|

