## 6. TRIAL DESIGN

### 6.1 Summary of Trial Design

#### Type of Trial summary:

A single centre, double blinded, randomised controlled trial comparing the effectiveness of two methods of foot shape capture currently used in NHS Orthotic services in Scotland. This is an Interventional, equivalence trial using medical devices (insoles).

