### **9.1 Description of Statistical Methods**

The change in FHSQ scores for the sub-domains of Pain, Foot Function, Foot Health and Footwear, will be compared between groups at the specified data collection time points: baseline, 4-weeks, 8-weeks and 12-weeks, using mix methods Analysis of Variance or Friedman tests with post hoc Wilcoxon tests for within group analysis and Mann-Whitney U tests for between group analysis if the data are not normally distributed.

The change in OPUS scores for the sub domain of Satisfaction With Device, will be compared between groups at the specified data collection time point of 12-weeks, using unpaired t-tests or Mann-Whitney U tests if the data are not normally distributed.

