### **9.2 The Number of Participants**

Power calculation for sample size: Based on data from Landorf et al. regarding FHSQ, a sample size was calculated to detect a clinically important difference between groups of 13 (SD = 26.9) points in Foot Health Status Questionnaire scores using the pain sub-domain as the primary outcome, giving a required minimum sample size of 54 participants in each group plus 5% drop out rate = 57 per group. Total sample size n=114.

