### **9.3 The Level of Statistical Significance**

Significance will be considered at P<0.5

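### The trial is labelled an equivalence trial, but its hypotheses, tests and sample size are those of a difference trial, with no margin or decision rule

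*Combined protocol and SAP*

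**What the plan says.** The design is declared twice. The synopsis gives "Interventional, equivalence Trial design", and section 6.1 repeats it: "This is an Interventional, equivalence trial using medical devices (insoles)".

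The statistics section describes something else:

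- **Section 9.0.2, null:** "The null hypothesis is that the change in FHSQ Pain score pre and post-treatment will not differ between the treatment groups".
- **Section 9.0.2, alternative:** "The alternative hypothesis is that the change in FHSQ pain score will differ between groups". No direction is given.
- **Section 9.1:** analysis of variance or, for non-normal data, Friedman and Wilcoxon tests within groups and "Mann-Whitney U tests for between group analysis if the data are not normally distributed". No confidence interval is compared with a limit.
- **Section 9.2:** "a sample size was calculated to detect a clinically important difference between groups of 13 (SD = 26.9) points", giving 54 per group, or 57 after 5% dropout and 114 in total. Power, significance level and sidedness are not stated.
- **Section 9.3:** "Significance will be considered at P<0.5", probably a misprint for 0.05. It is a significance threshold and nothing more.

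The nearest thing to a margin is in section 5: "The minimal important difference has a threshold of a 12.5 point change for pain". Neither that figure nor the 13 points in section 9.2 is called a margin. No section says how a non-significant result will be interpreted.

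**The concern.** In an equivalence trial the null hypothesis is that the arms differ by at least the margin, and the data must reject it. Section 9.0.2 has this the other way round: no difference is the starting assumption, and the data can only overturn it or fail to.

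Under that set-up, the only planned result that could be taken to support the declared aim is failure to reject. That does not control the chance of calling the methods equivalent when they differ by an amount the protocol itself treats as clinically important. It also rewards imprecision, because a smaller or noisier trial is more likely to find no difference. Section 4 says the results may guide practice and long-term service models, so a false equivalence claim would have consequences.

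**Working it through.** **Inputs.** Difference 13, SD 26.9, 54 per group before dropout and 57 after (section 9.2); minimal important difference 12.5 (section 5); 1:1 allocation (section 6.4.4).

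**Assumptions.** SD 26.9 is the SD of the change score (section 9.2 does not say). The significance level is 5%. A two-sample t-test approximates the section 9.1 analysis.

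**1. The plan's own figure.** For a two-sample t-test of 13 points with SD 26.9 and 80% power:

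- one-sided 5%: 54 per group, which matches section 9.2; 54/0.95 = 56.8, so 57 per group and 114 in total;
- two-sided 5%: 69 per group, which does not match.

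The 54 therefore fits a one-sided calculation, although the alternative in section 9.0.2 is two-sided. At two-sided 5%, 54 per group gives 70% power.

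**2. Reading non-significance as equivalence.** SE = 26.9 × √(2/54) = 5.177, with 106 degrees of freedom. Chance of a non-significant result with 54 per group:

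| True difference | Two-sided 5% | One-sided 5% |
|---|---|---|
| 13 | 29.9% | 19.8% |
| 12.5 | 33.3% | 22.5% |

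Two one-sided tests at 5% hold the corresponding error to 5% at the margin (4.9% computed for margin 12.5 and 54 per group).

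**3. Which observed results each rule would accept.**

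- Difference test, two-sided 5%: half-width 1.983 × 5.177 = 10.26. Observed differences up to about 10.3 points are non-significant.
- Equivalence at margin 12.5: 90% CI half-width 1.659 × 5.177 = 8.59. The interval fits only if the observed difference is below 12.5 − 8.59 = 3.91 points.

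Observed differences between about 3.9 and 10.3 points would be non-significant without showing equivalence.

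**4. Power of a proper equivalence test at the planned size** (two one-sided 5% tests, SD 26.9, allowing for estimation of the SD):

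| Margin | True difference | 54 per arm | 57 per arm |
|---|---|---|---|
| 12.5 | 0 | 54.9% | 58.8% |
| 13 | 0 | 60.5% | 64.2% |
| 12.5 | 3 | 47.9% | 51.2% |

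**5. Size for 80% power, true difference 0.** The normal approximation is n = 2 × [SD × (z₀.₉₅ + z₀.₉₀)/margin]². For margin 12.5 this is 2 × [26.9 × (1.645 + 1.282)/12.5]² = 79.3, so 80. The t-based calculation gives 0.79996 at 80 and 0.806 at 81. For margin 13 it gives 74 to 75, and for margin 10 about 125.

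**6. Sensitivity to the SD** (assumed values; margin 12.5, true difference 0):

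| SD | Power, 54 per arm | Per arm for 80% |
|---|---|---|
| 20 | 88.6% | 45 |
| 26.9 | 54.9% | 81 |
| 30 | 38.7% | 100 |

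**The case against.** The strongest reply is that equivalence appears only as a label. The primary objective is neutral: it compares changes in pain. Section 4 reports clinicians' doubts about like-for-like models and does not state an equivalence aim. The trial may simply be a mislabelled difference trial, and nothing says that a non-significant result will be called equivalence. That reading is possible, and the fix allows for it. But the label is there twice and the contradiction has to be resolved one way or the other.

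A second reply is that 54 per group is also what a non-inferiority calculation with a 13-point margin at one-sided 5% would give, so a margin-based intent cannot be excluded. True, but section 9.2 does not say so, section 9.0.2 is non-directional, and at SD 26.9 that size is too small for 80% power with two one-sided tests.

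A third is that the collected data could still support equivalence. They could, if a margin and an interval rule were fixed before unblinding. Section 9.6 only promises that deviations will be described and justified in the final report, which would not prevent a margin being chosen after the data are seen.

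Finally, the power figures depend on the SD and ignore any precision gained from repeated measures. This stands: at SD 20 the planned size would be ample. The missing margin and decision rule do not depend on the SD.

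**Conclusion.** The concern holds and must be fixed. Followed as written, the plan cannot support the conclusion its design label promises. If non-significance were taken as equivalence, the chance of passing a true 13-point difference would be about 30% at two-sided 5%, or 20% at one-sided 5%, against at most 5% under a proper equivalence test. These figures rest on 54 evaluable participants per arm, SD 26.9 as the SD of change, and a simple t-test. The contradiction itself rests on no assumption: the sections disagree on their face. Confidence is high.

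**What to change.** **If equivalence is intended:**

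- Section 9.0.2: make the null that the absolute between-group difference in FHSQ pain change is at least the margin, and the alternative that it is smaller. Name the time point. Twelve weeks fits the follow-up, but sections 5 and 9.1 list several time points, so this is a choice the team must make explicitly.
- Prespecify and justify the margin. The 12.5 points in section 5 is the document's own candidate and section 9.2 uses 13. Which, if either, is acceptable is a clinical judgement.
- Section 9.1: conclude equivalence only if the two-sided 90% CI for direct scan minus foam-box lies wholly inside the margin. If it crosses a limit, report equivalence as not shown. If it lies wholly outside, report a difference. Give an interval-based rule for the non-normal case too, since a Mann-Whitney p-value cannot serve.
- Section 9.2: replace the detection wording with the equivalence calculation, say what the SD refers to, and state power at the planned size.

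The cost is wording and a less favourable power statement: 55% to 59% for margin 12.5, or 60% to 64% for margin 13, at SD 26.9 and no true difference. Recruiting for 80% power instead would take 170 to 172 participants (80/0.95 gives 85 per arm; 81/0.95 gives 86) for margin 12.5, or 156 to 158 for margin 13. That would reopen the sample size and dates in section 2, the stopping rule in section 6.5 and the 12-month funding in section 14. It is an option, not a condition of the fix.

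**If a difference trial is intended:** remove the equivalence label from sections 2 and 6.1 and state that a non-significant result will not be reported as equivalence. This costs wording only, but gives up the equivalence claim.

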### **9.1 Description of Statistical Methods**

The change in FHSQ scores for the sub-domains of Pain, Foot Function, Foot Health and Footwear, will be compared between groups at the specified data collection time points: baseline, 4-weeks, 8-weeks and 12-weeks, using mix methods Analysis of Variance or Friedman tests with post hoc Wilcoxon tests for within group analysis and Mann-Whitney U tests for between group analysis if the data are not normally distributed.

The change in OPUS scores for the sub domain of Satisfaction With Device, will be compared between groups at the specified data collection time point of 12-weeks, using unpaired t-tests or Mann-Whitney U tests if the data are not normally distributed.

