**Code-Breaking:**

If the clinical condition of a participant necessitates breaking the allocation code, the Co-I (not blinded) will access the CAD/CAM insole ordering system to confirm the treatment-arm. This process will not unbind the whole trial, nor will it disclose the randomisation schedule.

Out of hours code-breaking will not be required due to the low risk level of the intervention.

At the end of the study the data from the two groups will be analysed independently, after which the groups will be relevelled.

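### Section 9.1 lets an undefined normality check choose the analysis, and its rank-based fallback names no single between-arm test and gives no difference in FHSQ points

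*Combined protocol and SAP*

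**What the plan says.** Section 9.1 states that change in the FHSQ sub-domains, pain included, "will be compared between groups at the specified data collection time points: baseline, 4-weeks, 8-weeks and 12-weeks". The method is given as "using mix methods Analysis of Variance or Friedman tests with post hoc Wilcoxon tests for within group analysis", followed by "Mann-Whitney U tests for between group analysis if the data are not normally distributed". I read the first option as a mixed (between-within) ANOVA.

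The section does not name a normality test, a threshold, the variable to be checked (raw score, change or residual), or what happens if one arm or visit fails the check and the others pass. OPUS satisfaction has the same kind of switch, from unpaired t-test to Mann-Whitney, at 12 weeks only.

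Four other places bear on this:

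- Section 9.0.2 frames a between-arm question: "The alternative hypothesis is that the change in FHSQ pain score will differ between groups".
- Section 5 lists the primary outcome as "Completed at the Second Appointment, Third Appointment, Fourth Appointment and Fifth Appointment", with no visit marked as primary.
- The Synopsis and Section 6.1 call the trial an equivalence trial. Section 9.2 sizes it on a 13-point difference (SD 26.9), with 54 per group before dropout.
- Section 6.4.4, under Code-Breaking, says: "At the end of the study the data from the two groups will be analysed independently". It adds that the groups are identified afterwards.

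**The concern.** There are two linked problems.

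First, the trial's own data choose the method, by a rule that is not written down. The research team, including the PI, carries out the analysis (Section 9.0.1), so an open rule leaves room for a choice made after the data have been seen. With about 54 per arm, moderate non-normality does not invalidate a linear-model estimate of a mean difference, so the switch buys little protection.

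Second, the fallback does not deliver what the trial needs. Its first part, "Friedman tests with post hoc Wilcoxon tests for within group analysis", tests change over time inside one arm and says nothing about the difference between arms. Its second part, Mann-Whitney, does compare arms. However, it is tied to no visit, and on its own it gives a P value with no estimate in FHSQ points. A rank P value cannot be set against a difference expressed in points. In the fallback, the trial could therefore finish without the one result that an equivalence claim rests on: a between-arm difference in FHSQ pain with a confidence interval.

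**Working it through.** **Inputs from the documents.** Difference 13 points, SD 26.9, 54 per arm before 5% dropout, 57 after (Section 9.2); baseline plus three follow-up assessments (Section 9.1).

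**Assumptions.** Two-sided 5% for each test, because Section 9.3 prints "Significance will be considered at P<0.5", which is a separate matter. Shapiro-Wilk at 5% on each arm-by-visit set, because no check is named. Correlation between visits of 0.3 to 0.7 for normal data, and 0.5 for bounded scores.

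**1. The plan's own sample size.** n per arm = 2 × SD² × (z for alpha + z for power)² / difference².
- One-sided 5%, 80% power: 2 × 26.9² × (1.645 + 0.842)² / 13² = 52.9, so 53. The t-based version gives 53.6, so 54, which matches.
- Two-sided 5%, 80% power: 2 × 26.9² × (1.960 + 0.842)² / 13² = 67.2, so 68, which does not match.
- Dropout: 54 / 0.95 = 56.8, so 57.

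The 54 is reproduced, with an alpha and power that the plan does not state. I use it below as the number per arm.

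**2. How often the fallback is triggered.** Three change scores in two arms make six checks. If the checks were independent and the data exactly normal, at least one rejects with probability 1 − 0.95⁶ = 26.5%. Simulation gives about 26% to 28%. With scores limited to 0-100 (SD 26.9; mean 50, or means rising from 45 to 65; continuous or in steps of 6.25), the figure for change scores is about 22% to 38%. If raw scores at four visits are checked instead (eight checks), normal data give about 31% to 35%, close to 1 − 0.95⁸ = 33.7%.

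**3. What the switch does to error at one visit.** The two-stage rule (check normality, then t-test or Mann-Whitney) gave false-positive rates of 4.1% to 5.9% over several settings with 1,500 runs each. The simulation standard error is √(0.05 × 0.95 / 1500) = 0.6 percentage points, so these are compatible with 5%. The t-test and Mann-Whitney gave different verdicts in 1.7% to 2.4% of null trials.

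**4. What several Mann-Whitney tests do.** If the test is run on change at 4, 8 and 12 weeks and any P below 0.05 counts:
- Independent tests: 1 − 0.95³ = 14.3%.
- Simulated, 54 per arm: about 12% to 13%, or 11% to 14% allowing for settings and simulation error.
- A single Mann-Whitney test at one visit: 4.8% to 5.0%.

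The figure hardly moves with the assumed correlation. All three changes share the same baseline, and with equal correlation r between visits, any two changes have correlation (1 − r) / [2(1 − r)] = 0.5, whatever r is.

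**5. What a points-scale result would give.** Taking 26.9 as the SD of the analysed score, the standard error of the difference is 26.9 × √(2/54) = 5.18 points, and the 95% half-width is 1.96 × 5.18 = 10.1 points. This interval is what a reader would compare with 13 points. The fallback as written does not produce it.

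**The case against.** The best defence is that Section 9.1 is governed by a between-group comparison, assigns Mann-Whitney to that purpose, and sits beside a between-group hypothesis. The switch is conventional, and step 3 shows that it barely affects the error rate at a single visit. That stands, and it limits the finding. Four stronger readings are tempting but not supported.

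- **That the verdict, and not only the method, turns on the normality check.** The choice of method may change often; the verdict at one visit rarely does.
- **That the fallback is almost certain to be used.** Rates above 90% can be obtained for raw scores limited to 0-100 with means rising from 45 to 65. Section 9.1 analyses change, for which the range is 22% to 38%.
- **That two significant within-arm improvements will be taken as equivalence.** The documents nowhere make within-arm significance the criterion. With assumed mean changes of 25 and 12 points, both arms would be significant in about 90% of trials despite a 13-point gap. This is illustration only: the plan gives no expected changes and does not say that 26.9 is the SD of within-person change.
- **That Section 6.4.4 prescribes separate analyses by arm.** The sentence is under Code-Breaking and leads on to identifying the groups, so it most naturally means that analysis comes before unblinding. It needs clearer wording and is weak evidence of anything more.

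Two further points stand. Testing at each visit is an inference, because the text does not say how many Mann-Whitney tests are run. The multiplicity also arises partly because no visit is primary, and the ANOVA route does not name its decisive term (presumably group-by-time) either. The gap is therefore not confined to the fallback. The criticisms about visits and within-arm tests do not apply to OPUS, which has one time point.

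**Conclusion.** The concern holds in a limited form and should be corrected. Section 9.1 leaves the choice of method to an undefined check on the trial's own data. On one branch there is no designated between-arm test and no estimate in FHSQ points.

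Under the assumed Shapiro-Wilk rule, that branch would be reached in roughly a quarter of trials with normal change scores and in about 22% to 38% with bounded ones, so it is a realistic route to the primary result. These rates depend on the assumed check, bounds, means and correlations, none of which the documents give.

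The main loss is the missing points-scale estimate with its confidence interval. The second is a chance of about 11% to 14% of at least one false positive, and this applies only if Mann-Whitney is run at all three follow-up visits without a multiplicity rule. Inflation of error by the switch itself is not part of the conclusion.

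**What to change.** - Remove the normality switch for the FHSQ. In all cases, use one pre-specified linear model for the between-arm difference in FHSQ pain change at a named visit (12 weeks, for example). Report it in points with a confidence interval, robust or bootstrap if residuals are skewed.
- Keep rank tests as sensitivity analyses. Label Friedman and Wilcoxon results as descriptive and state that they are not evidence of equivalence. Deleting them is not necessary.
- For OPUS, report the mean difference with a confidence interval whatever the normality result.
- Reword the sentence in Section 6.4.4 to say that arms coded A and B are compared in one analysis before the code is revealed.

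The cost is a wording amendment to Sections 9.1 and 6.4.4 and slightly more analysis work. No extra participants, visits or data are needed.
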